APPENDIX III: STUDY PARAMETERS AND ASSESSMENTS

Table 5.0: Pre-treatment assessments

Assessment	Time Points
	≤ 30 days prior to registration
Evaluation by a radiation oncologist	X
Evaluation by a medical oncologist	X
History/physical examination	X
Performance Status (ECOG)	X
CBC w/ diff & ANC, platelets, ALT, AST	≤ 30 days prior to registration.
Serum/urine pregnancy test (if applicable)	≤ 14 days prior to registration
CT Scans of the chest/abdomen/pelvis with radionuclide bone scan OR whole body PET/CT	X
Histological confirmation from at least one metastasis	x
MRI of the vertebral column	If vertebral column metastases identified on staging and will be treated

Table 6.0: Post-Treatment Assessments**ASSESSMENTS IN FOLLOW-UP**

Assessment	Time Points	
	30 days after completion of SBRT	Every 3 months after completion of SBRT for a total of 2 years
Physical examination	X	X
Evaluation by a radiation oncologist	X	X
Performance status	X	X
ALT, AST, Total and Direct Bilirubin	X (If SBRT delivered to the liver)	X (If SBRT delivered to the liver) Perform at 3 months then every 6 months
Hgb	Recommended if clinical symptoms of anemia on physical exam post-treatment	
Diagnostic Imaging		X Per protocol or if clinically warranted
Adverse event evaluation	X	X

LIST OF COMMON ABBREVIATIONS AND DEFINITIONS OF TERMS

ADL	Activities of Daily Living
AE	Adverse event
AESI	Adverse event of special interest
ALP	Alkaline phosphatase
ALT	Alanine aminotransferase
ANA	Antinuclear antibody
ANC	Absolute neutrophil count
aPTT	Activated partial thromboplastin time
ARGUS	Pharmacovigilance and clinical safety software system
AST	Aspartate aminotransferase
AUC	Area under the concentration–time curve
BAL	Bronchoalveolar lavage
BC	Breast cancer
BUN	Blood urea nitrogen
CPA	Cyclophosphamide
CR	Complete response
CRF; eCRF	Case report form (electronic or paper); electronic case report form
CRO	Contract research organization
CRP	C-reactive protein
CT	Computed tomography
CTLA-4	Cytotoxic T-lymphocyte antigen 4
CTV	Clinical target volume
(NCI-) CTCAE	(National Cancer Institute) Common Terminology Criteria for Adverse Events
DLT	Dose-limiting toxicity

Dmax Maximum radiation dose

EC Ethics committee

ECG Electrocardiogram

EDC Electronic data capture

FDG-PET 18F-fluorodeoxyglucose positron emission tomography

FFPE Formalin-fixed, paraffin-embedded

FNA Fine-needle aspirate

fx Fraction(s)

GCP Good clinical practice

GBM Glioblastoma multiforme

GM-CSF Granulocyte-macrophage colony-stimulating factor

GTV Gross target volume

H&N Head and neck

HPV human papillomavirus

HLA Human leukocyte antigen

ICF Informed consent form

ICH International Conference on Harmonisation

IHC Immunohistochemistry

INR International Normalized Ratio

irRC Immune-related response criteria

IRB Institutional Review Board

irAE Immune-related adverse event

ITV. Internal target volume

IUD Intrauterine device

IV Intravenous

LC Local control

LD Longest diameter

LE Local enlargement

LDH Lactate dehydrogenase

LDL Low-density lipoprotein

LLOQ Lower limit of quantification

mAb Monoclonal antibody

Max Vol Maximum (tissue) volume

MedDRA Medical Dictionary for Regulatory Activities

monoRX Monotherapy

MRI Magnetic resonance imaging

MTD Maximum tolerated dose

NCI-CTCAE National Cancer Institute-Common Terminology Criteria for Adverse Events

NOAEL No-observed-adverse-effect level

NSCLC Non-small-cell lung cancer

PBMC Peripheral blood mononucleated cell

PD-1 Programmed death-1 (receptor)

PD-L1, PD-L2 Programmed death ligand 1, programmed death ligand 2

PET Positron-emission tomography

PK Pharmacokinetic

PR Partial response

PT Preferred term

PTV Planning target volume

RBC Red blood cell

RCC Renal cell cancer

RECIST Response Evaluation Criteria in Solid Tumors**Regeneron Regeneron Pharmaceuticals, Inc.****RF Rheumatoid factor****RILD Radiation-induced liver disease****RP2D Recommended phase 2 dose****SAE Serious adverse event****SAF Safety analysis set****SAP Statistical analysis plan****SAS Statistical Analysis Systems (software)****SABR Stereotactic Ablative Radiotherapy****SBRT Stereotactic Body Radiotherapy****SCHNC squamous-cell head and neck cancer****SOC System organ class****SSA Sjögren's syndrome A antigen****SSB Sjögren's syndrome B antigen****t_{1/2} Beta-phase terminal half life****TEAE Treatment-emergent adverse event****TSA a mouse mammary adenocarcinoma cell line****TSH Thyroid-stimulating hormone****WBC White blood cell****XRT Radiotherapy**

REFERENCES

Since the development of this study, additional data regarding immunotherapy has emerged. Additional immunotherapy agents have shown efficacy in the treatment of metastatic NSCLC in the first line setting. Pembrolizumab is a humanized monoclonal antibody against the PD-1 with antitumor activity in advanced NSCLC expressing PD-L1. The Keynote-024 trial compared previously untreated advanced NSCLC with PD-L1 expression on at least 50% of tumor cells and no sensitizing mutation of the epidermal growth factor receptor gene or translocation of the anaplastic lymphoma kinase gene to receive either Pembrolizumab (at a fixed dose of 200 mg every 3 weeks) or the investigator's choice of platinum-based chemotherapy (1). Median progression free survival, 6 month overall survival and response rate were significantly improved in the Pembrolizumab arm. Pembrolizumab has now redefined initial systemic therapy for PD-L1 expressing tumors in the metastatic setting.

We hereby propose that immunotherapy in this trial now include Nivolumab or Pembrolizumab as long as patients are eligible.

References

1. Reck M et al. *N Engl J Med.* 2016 Nov 10;375(19):1823-1833. Epub 2016 Oct 8.

STUDY ADDENDUM 2.

Since the last re-authorization of the study, there have been several changes in the immunotherapy landscape from randomized phase III trials. These changes affect our proposed utilization of stereotactic body radiation therapy (SBRT) and immunotherapy in 17-009.

First line systemic therapy for metastatic lung adenocarcinoma now includes combination chemotherapy and immunotherapy. Keynote-189 showed an improved overall survival with pembrolizumab/alimta and carboplatin vs carboplatin/alimta alone (1). This survival benefit was higher with increasing PD-L1 expression but was maintained regardless of PD-L1 expression. Similarly, Key-407 showed an improved overall survival in patients with metastatic squamous cell lung carcinoma with combination carboplatin/taxol/pembrolizumab vs carboplatin/taxol alone (2) with PD-L1 expression $\geq 1\%$. Additionally, the PACIFIC trial showed an significant increase in overall survival in patients with stage III non-small cell carcinoma when Darvalumab was added following concurrent chemoradiation vs observation (3).

With these changes in the immunotherapy landscape, it is highly likely that patients with lung cancer will be increasingly exposed to immunotherapy agents earlier in the treatment course making them ineligible for our study since we currently exclude patients with prior immunotherapy treatments.

Early data with sequential or combination SBRT suggest increased immunotherapy efficacy with similar rates or minimal changes in the toxicity profile of immunotherapy agents (4-5). Since our initial eligibility criteria was designed to limit excess patient toxicity and current available data suggests a combination/sequential regimen is safe, it is prudent that we revise our inclusion/exclusion criteria.

We hereby propose that patients with prior/ongoing immunotherapy treatment be eligible for participation in this study. The eligibility criterion has been modified as such to reflect this change.

References

1. Ghandi L. et al. Pembrolizumab plus Chemotherapy in Metastatic Non-Small-Cell Lung Cancer. *N Engl J Med* 2018; 378:2078-2092
2. Lopes G. et al. Pembrolizumab (pembro) versus platinum-based chemotherapy (chemo) as first-line therapy for advanced/metastatic NSCLC with a PD-L1 tumor proportion score (TPS) $\geq 1\%$: Open-label, phase 3 KEYNOTE-042 study. *J Clin Oncol* 36, 2018 (suppl; abstr LBA4).
3. AstraZeneca Press Release 05/2018: <https://www.astrazeneca.com/media-centre/press-releases/2018/imfinzi-significantly-improves-overall-survival-in-the-phase-iii-pacific-trial-for-unresectable-stage-iii-non-small-cell-lung-cancer-25052018.html>

4. Theelen W. et al. Randomized phase II study of pembrolizumab after stereotactic body radiotherapy (SBRT) versus pembrolizumab alone in patients with advanced non-small cell lung cancer: The PEMBRO-RT study. *J Clin Oncol* 36, 2018 (suppl; abstr 9023)
5. McArthur H. et al. A phase II, single arm study assessing the efficacy of pembrolizumab (Pembro) plus radiotherapy (RT) in metastatic triple negative breast cancer (mTNBC). *J Clin Oncol* 36, 2018 (suppl; abstr 9023)

CLINICAL STUDY PROTOCOL

Protocol Title: A PROSPECTIVE TRIAL OF IMMUNOTHERAPY AND STEREOTACTIC BODY RADIOTHERAPY (SBRT) FOR THE TREATMENT OF METASTATIC LUNG CANCER: SBRT SENSITIZATION OF THE PROGRAMMED DEATH-1 (PD-1) EFFECT

VERSION 6.0, 06/18/2018

Clinical Phase: Pilot/Phase II

Hypothesis: The addition of Stereotactic Body Radiation Therapy sequenced prior to PD-1/PD-L1 blockade leads to increased immunogenicity and immune system response. Increased response should translate to increased progression free survival and improved survival relative to PD-1 blockade monotherapy in metastatic lung cancer.

Principal Investigator

[name]

Department of Radiation Oncology

Crozer Keystone Health System/Philadelphia CyberKnife Center

[name]

confidential: This document contains confidential information that is the property of Precision Radiation Oncology and must not be disclosed to anyone other than designees of Precision Radiation Oncology for conduct of the study, clinical investigators and members of the Institutional Review Board.

STUDY ADDENDUM 2.

Since the last re-authorization of the study, there have been several changes in the immunotherapy landscape from randomized phase III trials. These changes affect our proposed utilization of stereotactic body radiation therapy (SBRT) and immunotherapy in 17-009.

First line systemic therapy for metastatic lung adenocarcinoma now includes combination chemotherapy and immunotherapy. Keynote-189 showed an improved overall survival with pembrolizumab/alimta and carboplatin vs carboplatin/alimta alone (1). This survival benefit was higher with increasing PD-L1 expression but was maintained regardless of PD-L1 expression. Similarly, Key-407 showed an improved overall survival in patients with metastatic squamous cell lung carcinoma with combination carboplatin/taxol/pembrolizumab vs carboplatin/taxol alone (2) with PD-L1 expression $\geq 1\%$. Additionally, the PACIFIC trial showed an significant increase in overall survival in patients with stage III non-small cell carcinoma when Darvalumab was added following concurrent chemoradiation vs observation (3).

With these changes in the immunotherapy landscape, it is highly likely that patients with lung cancer will be increasingly exposed to immunotherapy agents earlier in the treatment course making them ineligible for our study since we currently exclude patients with prior immunotherapy treatments.

Early data with sequential or combination SBRT suggest increased immunotherapy efficacy with similar rates or minimal changes in the toxicity profile of immunotherapy agents (4-5). Since our initial eligibility criteria was designed to limit excess patient toxicity and current available data suggests a combination/sequential regimen is safe, it is prudent that we revise our inclusion/exclusion criteria.

We hereby propose that patients with prior/ongoing immunotherapy treatment be eligible for participation in this study. The eligibility criterion has been modified as such to reflect this change.

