2.0 PROPOSED TRIAL RATIONALE

Anti-PD-1 antibodies have demonstrated activity in the treatment of lung cancer. Opdivo was approved in February of 2015 by the FDA for patients with metastatic squamous NSCLC with progression on or after platinum based therapy. In the open-label trial, patients were randomized to receive OPDIVO (n=135) administered at 3mg/kg every 2 weeks. Median survival was improved to 9.2 months compared to 6 months in patients receiving docetaxel (n=137) 75mg/m² every 3 weeks, p=0.00025. Median progression free survival was slightly improved to 3.5 months compared to 2.8 months but 1 year overall survival was improved to 42% compared to 24% (36).

We expect that improvements in local control, increased immunogenic response and abscopal effect seen with combined modality treatment will result in improved local control, progression free survival and resultant significant increases in overall survival beyond 3 months. We propose a pilot/phase II study to assess the safety and efficacy of combination immunotherapy and stereotactic ablative radiation therapy (I-SABR).

Treatment will be a sequential combination treatment of SABR/SBRT and immunotherapy to assess the safety and feasibility of treatment. SABR/SBRT will be administered in 3-5 daily treatments followed by immunotherapy following the conclusion of SABR/SBRT. This approach will take advantage of the transient increase in antigen availability, increased antigen presentation and upregulation of PD-1 by tumor cells following ablative radiation therapy. After an interim safety analysis, the study will continue to the phase II portion where overall survival, progression free survival and response rate will be the primary and secondary end points. For reference, outcomes will be compared to the immunotherapy arms of checkmate 057 and Keynote 042 trials.

Several trials examining combination I-SABR are currently underway. A table of selected studies is included in [Table 1](#).

Study (Institution)	SABR Target	Dose (Gy/Fractionation)	Immunotherapy Agent	Sequence
NCT02239900 (MD Anderson Cancer Center)	Liver Lung Adrenal	50/4 60/10	Ipilimumab	Concurrent/Sequential
NCT01862900 (Chiles Research Institute)	Lung Liver	15/1 201/1	Anti-OX40	Concurrent
NCT01769222 (Stanford University)	Any	20/2	Ipilimumab	Concurrent
NCT02298946 (NIH/NCI)	Liver	8/1 24/3	PD-1 Inhibitor	Sequential

Table 1. List of selected ongoing I-SABR studies

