3. STUDY OBJECTIVES

3.1 Primary Objectives

The primary objective of the pilot phase of the study is to characterize the safety, feasibility and tolerability of sequential combination I-SABR in patients with metastatic NSCLC. The first 20 patients will be evaluated for 15 weeks following treatments with I-SABR prior to continuing enrollment. In the Brahmer trial, 5% of patients in the Nivolumab arm developed pneumonitis with a median time to onset of treatment related pulmonary events of 15 weeks. All but one patient with pulmonary events were treated with glucocorticoids and all cases resolved with a median time to resolution of 5 weeks (range 0.6-12.1 weeks).

If more than 5% of patients develop grade ≥ 3 pneumonitis during the initial evaluation phase, no lung directed therapy will be permitted during the phase II portion.

The primary objective of the phase II portion of the study will be overall survival.

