5.3 Sample Size

More than 350 patients with metastatic lung cancer present to the Crozer-Keystone health system for treatment annually. If 50% of patients are eligible for this study, we expect approximately 100 patients will enroll and be treated on this study. Patients will be followed for 2 years on the study. The study will conclude 2 years after the last patient is enrolled. An interim safety and feasibility analysis will be performed on the first 20 patients in the pilot phase. Overall survival, progression free survival, local control and subgroup analysis will be performed on the entire patient cohort at the conclusion of the study.

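### The plan is framed as SBRT before PD-1/PD-L1 blockade but pools in patients already on blockade, so the pooled survival result, and any pilot pneumonitis rate that includes them, do not describe the stated sequence

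*Protocol*

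**What the plan says.** **The stated sequence.** The Version 6.0 hypothesis reads: "The addition of Stereotactic Body Radiation Therapy sequenced prior to PD-1/PD-L1 blockade leads to increased immunogenicity and immune system response". It goes on to expect "improved survival relative to PD-1 blockade monotherapy in metastatic lung cancer". Section 2.0 gives the order, "SABR/SBRT will be administered in 3-5 daily treatments followed by immunotherapy following the conclusion of SABR/SBRT", and the reason for it: "This approach will take advantage of the transient increase in antigen availability". The pilot objective in section 3.1 is to "characterize the safety, feasibility and tolerability of sequential combination I-SABR in patients with metastatic NSCLC".

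**Who may enter.** Study Addendum 2 says: "We hereby propose that patients with prior/ongoing immunotherapy treatment be eligible for participation in this study". Inclusion criterion 2, in section 5.1 and in the revised criteria, admits patients with earlier immunotherapy and patients whose disease has progressed on it, if the progressing sites can be treated locally. Section 4.3 accepts immunotherapy before SBRT. Section 7 lets immunotherapy either begin or carry on once SBRT is finished.

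**How patients are analysed.** Section 3.1 applies one pneumonitis rule to the first 20 patients together: if more than 5% have grade 3 or higher pneumonitis, lung-directed treatment is not allowed in phase II. Section 8.2 stratifies by number of lesions, and the only subgroup objective in section 3.2 concerns the number of metastatic sites. Section 5.3 says: "Overall survival, progression free survival, local control and subgroup analysis will be performed on the entire patient cohort". Section 2.0 reads the outcomes against the immunotherapy arms of two other trials.

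**The concern.** Addendum 2 changed who may enter. The hypothesis, the pilot objective, the pilot rule, the stratification and the external comparison were not adapted to match. For a patient on ongoing blockade the drug came first and SBRT was added to it, which is not the order that the hypothesis names.

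Two conclusions are at stake. The pooled overall survival result would be read as evidence on SBRT before blockade, compared with blockade alone, although an unknown share of the cohort had a different order of treatment. And the pilot pneumonitis rate decides whether lung-directed SBRT continues in phase II; if it mixes new starters with pre-exposed patients, it is not the rate for the regimen named in the pilot objective.

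**Working it through.** **1. Can a patient be irradiated during blockade?** Section 2.0 cites nivolumab every 2 weeks and Addendum 1 cites pembrolizumab every 3 weeks. SBRT is given in 3-5 daily treatments, so a course can fit between two doses. The only interval rule in section 5.2 (item 8, 4 weeks) concerns investigational drugs in another trial. The text therefore permits SBRT during blockade.

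**2. Does the plan separate these patients?** The pilot rule is one pooled rate. Stratification and the subgroup objective use lesion or site number. The assessment tables in Appendix III list neither immunotherapy exposure nor dose dates as items. The subgroup analysis mentioned in section 5.3 is not defined.

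**3. How much does the mix matter for the pilot rule?** More than 5% of 20 means at least 2 events, since 1/20 is exactly 5%.

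Inputs from section 3.1: n = 20 and the 5% threshold. Assumptions, because the documents give no figures: a true rate of 10% in new starters, the share pre-exposed, and the relative risk (RR) of grade 3 or higher pneumonitis in pre-exposed patients against new starters.

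All new starters:

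P(≥2) = 1 − 0.9^20 − 20 × 0.1 × 0.9^19 = 1 − 0.1216 − 0.2702 = 0.608.

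Ten new starters at 10% and ten pre-exposed at 5% (RR 0.5):

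- P(0) = 0.9^10 × 0.95^10 = 0.3487 × 0.5987 = 0.2088
- P(1) = 0.3874 × 0.5987 + 0.3487 × 0.3151 = 0.3418
- P(≥2) = 1 − 0.2088 − 0.3418 = 0.449

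The same calculation over the range of assumptions gives the chance that the rule is triggered:

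| Pre-exposed among 20 | RR 0 | RR 0.5 | RR 1 | RR 1.5 | RR 2 |
|---|---|---|---|---|---|
| 5 (25%) | 45.1% | 53.3% | 60.8% | 67.6% | 73.6% |
| 10 (50%) | 26.4% | 44.9% | 60.8% | 73.4% | 82.7% |
| 15 (75%) | 8.1% | 35.8% | 60.8% | 78.3% | 89.0% |

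With half the pilot pre-exposed, the expected pooled rate is 10% × (1 + RR)/2: 5%, 7.5%, 10%, 12.5% and 15% across the columns. The rule is sensitive to the mix, and the direction turns on whether RR is below or above 1.

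**4. Overall survival.** The documents give nothing from which to size the effect of mixing. A patient who enters on blockade has survived on it to that point; one who enters after progressing on it has already failed it. These could pull the pooled result in opposite directions, so no direction is claimed.

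**The case against.** **The pilot rate need not be too low.** A reader might infer that pre-exposed patients have already tolerated the drug, so the pilot rate is diluted and understates the risk in new starters. That direction is plausible: section 3.1 cites a median onset of 15 weeks for drug-related pulmonary events, and section 5.2 excludes unresolved toxicity. The documents do not establish it. Resolved pneumonitis is not excluded, Addendum 2 sets no minimum time on drug, and the rule counts all grade 3 or higher pneumonitis, including any part due to radiation. No passage gives a rate in pre-exposed patients. This stands, and the point is limited to possible bias.

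**The pilot may be unaffected.** Addendum 2 says that patients with prior immunotherapy were excluded until then, and it amends a study already authorised. The first 20 patients could all be new starters. This also stands; it would remove the pneumonitis part and leave the survival part.

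**Sequence was never testable.** A reader might infer that Addendum 2 stopped the trial from testing sequence. It did not: the design is single-arm, no objective compares sequences, and neither new starters alone nor the split proposed here could do so. What remains is that the treated cohort no longer matches the sequence in the hypothesis.

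**The broadening is deliberate, and the rest may be in the SAP.** Addendum 2 gives its reasons and the body text follows it; the eligibility choice is not criticised here. An exposure subgroup or dose dates may appear in an SAP or case report form not shown. But the pooled pilot rule, the lesion-only stratification and the mismatch between hypothesis and section 7 are fixed in the protocol, and an SAP would not remove that mismatch.

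**Conclusion.** The point holds as an internal mismatch with consequences for what the trial can conclude. The hypothesis, rationale and pilot objective describe SBRT before blockade; the eligibility criteria and section 7 admit SBRT during blockade; the analysis pools the two. The pooled survival result does not describe the stated sequence, and neither does the pilot pneumonitis rate if any of the first 20 were pre-exposed.

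The effect on the pilot rule could be large: against 61% for an all-new pilot, the trigger chance runs from 26% to 83% with half pre-exposed. Those figures rest wholly on an assumed 10% rate, an assumed share and an assumed relative risk. They show sensitivity, not a demonstrated bias. An amendment is worthwhile because the remedy is cheap and treatment dates not collected as patients enter may be hard to recover.

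**What to change.** - Record the date of the last immunotherapy dose before SBRT and of the first dose after it.
- Define two groups: blockade started after SBRT, and blockade ongoing at SBRT. State in which group a patient with earlier, completed immunotherapy is counted.
- Report the pilot pneumonitis numerator and denominator, and overall survival, for each group, and state how many of the first 20 patients enrolled under Addendum 2.
- Base any conclusion about SBRT before blockade on the first group. Label the second as SBRT added to ongoing blockade.
- Reconcile the Version 6.0 hypothesis and the word sequential in section 3.1 with section 7 and Addendum 2.

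The cost is two dates on the case report form and amendment wording. The downside is fewer patients behind the SBRT-first conclusion and a less precise pilot rate in each group. No washout, interval or treatment change is proposed.
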